## **2.4 REGISTRATION PROCEDURES**

Authorized staff must register an eligible candidate with NCI Central Registration Office (CRO) within 24 hours of signing consent. A registration Eligibility Checklist from the web site (<http://home.ccr.cancer.gov/intra/eligibility/welcome.htm>) must be completed and sent via encrypted email to: NCI Central Registration Office [[contact]](mailto:[contact]).

After confirmation of eligibility at Central Registration Office, CRO staff will call pharmacy to advise them of the acceptance of the patient on the protocol prior to the release of any investigational agents. Verification of Registration will be forwarded electronically via e-mail to the research team.

#### 2.4.1 Treatment Assignment Procedures

#### Cohorts

Number	Name	Description
1	Solid Tumors HER2-directed therapies naïve dose escalation cohort	Patients with ovarian, cervical, colon, non-small cell lung, renal cell, bladder, malignant soft tissue and bone tumor, prostate cancer or other solid tumors as well patients with breast cancer to be treated with AdHER DC vaccine at escalating doses.
2	Solid Tumors HER2-directed therapies naïve expansion cohort	Patients with ovarian, cervical, colon, non-small cell lung, renal cell, bladder, malignant soft tissue and bone tumor, prostate cancer or other solid tumors as well patients with breast cancer to be treated with AdHER DC vaccine at $40 \times 10^6$ dendric cells maximum.
3	Solid Tumors with prior HER2-directed therapies dose escalation cohort	Patients with recurrent or progressive, metastatic breast cancer, gastric/gastroesophageal or other cancers treated with AdHER DC vaccine at Dose Level 1.
4	Solid Tumors with prior HER2-directed therapies expansion cohort	Patients with recurrent or progressive, metastatic breast cancer, gastric/gastroesophageal or other cancers enrolled in dose expansion cohort.

#### Arms

Number	Name	Description
1	Part I dose escalation	AdHER DC vaccine administered at escalating doses.
2	Part I dose expansion	AdHER DC vaccine administered at $40 \times 10^6$ dendric cells maximum.
3	Part II dose escalation	AdHER DC vaccine administered at Dose Level 1.
4	Part II dose expansion	AdHER DC vaccine administered at $40 \times 10^6$ dendric cells maximum.

#### Randomization and Arm Assignment

There will be no randomization on this study.

Up to 18 patients in Cohort 1 will be assigned to Arm 1

Up to 12 patients in Cohort 2 will be assigned to Arm 2

Up to 6 patients in Cohort 3 will be assigned to Arm 3

Up to 24 patients in Cohort 4 will be assigned to Arm 4

## **2.5 BASELINE EVALUATION**

Below studies will be obtained within 30 days prior to the administration of the first dose of vaccine. If any of the studies were performed on another protocol, they may not need to be repeated.

- CBC with Differential
- Acute care panel, hepatic panel, mineral panel, total protein, amylase, lipase, uric acid
- PT/PTT
- Lipid panel
- Immunoglobulin quantification, IgE
- LDH
- CPK, Troponin I
- Thyroid screen (TSH, Free T4)
- 25-OH-vitamin D
- Lymphocyte subsets
- Tumor markers (optional)
- Urinalysis
- ABO typing and HLA A, B, C and DR (if not done in NIH Clinical Center in the past)
- CT CAP (to be done only if screening scans were performed at an outside institution and not repeated at the NCI).
- MRI Brain (to be done only if clinically indicated and screening scans were performed at an outside institution and not repeated at the NCI).
- CT Neck (to be done only if clinically indicated and screening scans were performed at an outside institution and not repeated at the NCI).
- Bone Scan (to be done only if patient has bone metastasis and screening scans were performed at an outside institution and not repeated at the NCI).
- Echocardiogram (to be done only if screening echo(s) were performed at an outside institution and not repeated at the NCI).

## **3 STUDY IMPLEMENTATION**

### **3.1 STUDY SCHEMA AND DESIGN**

This is an open label, single site, non-randomized, two-part, phase I study of an autologous dendritic cell (DC) vaccine transduced with AdHER2 to determine vaccine safety, immunogenicity and preliminary activity. The study design schema is outlined in [Figure 11](#).

Once enrollment eligibility is confirmed and informed consent is obtained, the patient will be scheduled for an apheresis of up to 18 liters to collect mononuclear cells by counter-flow elutriation, aliquoted into minimum of 6 vials with up to  $333 \times 10^6$  cells/vial that will be cryopreserved for future preparation of the autologous AdHER2 DC vaccine product. If the collected apheresis products are not adequate for 5 doses of vaccine, the patient may undergo

additional apheresis per investigator's discretion. Co-enrollment in the Indium trastuzumab imaging protocol 07-C-0101 will be offered to those patients that are interested and eligible.

Note: In order to be cleared for the next treatment, a safety visit (i.e., physical and clinical laboratory assessments, review of toxicities/adverse events) must occur within 7 days prior to the treatment. Treatment visits can also be safety visits for previous injections. This is so the treating physician will evaluate the patient for toxicities potentially caused by previous injections.

### Part I N = 30 patients

Part I of the study will investigate vaccine dose escalation in adults with recurrent or progressive, metastatic solid tumors as well as adjuvant bladder cancer patients whose tumors are characterized by some HER2/neu expression but for whom trastuzumab is *not* clinically indicated:

- Patients with ovarian, cervical, colon, non-small cell lung, renal cell, bladder, malignant soft tissue and bone tumor, prostate cancer or other solid tumors that is known to be HER2 1+, 2+ or 3+ by IHC OR have a Vysis FISH result  $\geq 1.8$ .
- Patients with breast cancer that is known to be HER2 2+ or 3+ or with an equivocal or positive FISH result.

**NOTE:** Adjuvant bladder cancer patients will not be enrolled in Part I of the study until AdHER2 DC vaccine safety has been demonstrated out to 12 Weeks in at least 10 patients.

The goal of Part I is to determine whether there is a preliminary significant, adverse safety signal regarding cardiac toxicity in this patient population that is *naive to HER2-directed therapies*, in addition to preliminary assessment of the vaccine's immunogenicity and clinical activity.

Allowable tumors include breast, ovarian, colon, non-small cell lung, renal cell, bladder and prostate cancer. Inclusion of a broad spectrum of tumors that express HER2 will facilitate more rapid accrual and allow prompt determination of the vaccine's safety and immunogenicity. However, the inclusion of subjects with multiple tumor types that have varying levels of HER2 expression may preclude identification of an optimal biologically active dose.

### Proposed Dosage and Administration

This part of the study will enroll patients in the vaccine dose levels outlined below:

Dose Level 1 (N = 6 patients):	$5 \times 10^6$ viable cells/vaccine
Dose Level 2 (N = 6 patients):	$10 \times 10^6$ viable cells/vaccine
Dose Level 3 (N = 6 patients):	$20 \times 10^6$ viable cells/vaccine
Expansion Cohort (N = 12 patients):	$40 \times 10^6$ viable cells/vaccine

Autologous AdHER2 DC vaccine will be administered intradermally at Weeks 0, 4, 8, 16 and 24. Response will be measured as outlined in section [6.2](#). Vaccine dose escalation will follow the procedures specified in Section [3.1.2](#).

### Part II N = 30 patients

Part II of the study will be conducted in adults with recurrent or progressive, metastatic breast cancer, gastric/gastroesophageal or other cancers with 1+ to 3+ HER2/neu expression by IHC or an equivocal or positive FISH result. Vaccine dose escalation (as required by the FDA) will be repeated in an identical manner *in a population with prior exposure to trastuzumab, pertuzumab, lapatinib, ado-trastuzumab emtansine (TDM1) and other HER2-directed therapies* to again determine whether there is an adverse safety signal regarding cardiac toxicity, in addition to assessment of the vaccine's immunogenicity and clinical activity. Vaccine administration and

re-staging assessment is identical to that conducted in Part I with revised vaccine dosing as outlined below and in Section **3.1.2**.

### **Proposed Dosage and Administration**

Part II of the study will enroll 30 breast, gastric/gastroesophageal or other cancer patients as outlined in the vaccine dose cohorts outlined below:

Dose Level 1 (N = 6 patients):  $20 \times 10^6$  *viable* cells/vaccine

Expansion Cohort (N = 24 patients):  $40 \times 10^6$  *viable* cells/vaccine

Autologous AdHER2 DC vaccine will be administered intradermally at Weeks 0, 4, 8, 16 and 24. Re-staging will be performed as outlined in Section **6.2**. Vaccine dose escalation will follow the revised procedures specified in Section **3.1.2**.

Abbreviated Title: AdHER2/neu DC Vaccine

Version Date: 07/22/2019

Figure 11: AdHER2 Autologous DC Vaccine Study Schema

	Screen Consent Baseline	Week 0	Week 4	Week 8	Week 12	Week 16	Week 20	Week 24	Week 28	Week 32	Week 36	Week 40	Week 48	Week 60	Week 76	Week 100	Week 124
Vaccine		V	V	V	V	V	V										
Echo	V		V	V	V	V	V	V	V	V	V	V	V	V	V	V	V
Scans	V			V	V	V	V	V	V	V	V	V	V	V	V	V	V
Correlatives	V			V	V	V	V	V	V	V	V	V	V	V	V	V	V

### 3.1.1 Dose Limiting Toxicity

The following assessment guidelines for the management of dose limiting toxicity (DLT) are intended to ensure the safety of each patient while on the study. The descriptions and grading scales found in the revised NCI Common Terminology Criteria for Adverse Events (CTCAE) version 4.0 will be utilized for AE and DLT reporting. All appropriate treatment areas should have access to a copy of the CTCAE version 4.0. A copy of the CTCAE version 4.0 can be downloaded from the CTEP web site ([http://ctep.cancer.gov/protocolDevelopment/electronic\\_applications/ctc.htm#ctc\\_40](http://ctep.cancer.gov/protocolDevelopment/electronic_applications/ctc.htm#ctc_40)).

All adverse events will be classified as follows for determination of relatedness to AdHER2 vaccination:

- Unrelated
- Unlikely
- Possibly related
- Probably related
- Definitely related

For the purposes of this study, the definitions of dose limiting-toxicities include:

- CTCAE Grade 2 and greater allergic reactions
- CTCAE Grade 2 and greater autoimmune disorders
- CTRCD, defined as a decrease in the LVEF of > 10 percentage points, to a value in < 53%. Documentation of the above specified change in LVEF will require cardiac consultation for determination of clinical significance. Cardiac function deterioration clinically associated with apparent cardiotoxic agent use after off-therapy will be censored at the point of cardiotoxic agent use.
- CTCAE Grade 3 or greater organ toxicity (dermatologic, gastrointestinal, hepatic, pulmonary, renal/genitourinary, or neurologic) occurring within 30 days of vaccine administration that are at least possibly related to research in.

### **Immunization-Related Dose Limiting Toxicity:**

- CTCAE Grade 3 and greater anaphylaxis: symptomatic bronchospasm with or without urticaria; parenteral intervention indicated; allergy-related edema/angioedema; hypotension (Grade 3). Life threatening consequences; urgent intervention indicated (Grade 4).
- CTCAE Grade 3 and greater injection site reactions: ulceration or necrosis; severe tissue damage; operative intervention indicated (Grade 3). Life threatening consequences; urgent intervention indicated (Grade 4).

### **Early stopping rules for accrual will be invoked in each part of the study if:**

- **Two or more of 6 patients in a given dose level develop evidence of cardiac toxicity, accrual will be stopped to that dose cohort. Accrual expansion of an additional 12 patients will occur in the next lower dose level to further evaluate for cardiac toxicity.**
- **Any death (unrelated to underlying primary disease) that occurs and is attributed as being possibly, probably or definitely related to the investigational AdHER2 DC vaccine (FDA requirement)**

### 3.1.2 Dose Escalation

It has been reported that up to 7% of patients with HER2/neu expressing tumors treated with trastuzumab monotherapy for metastatic breast cancer developed clinically significant cardiac dysfunction including congestive heart failure. It would be considered acceptable if the therapeutic AdHER2 vaccine proposed for this study would produce no greater than that level of cardiac toxicity, but not if it were to be exceeded. In order to evaluate this using a limited number of patients, a two-part design, but incorporating an early stopping rule, will be implemented. The goal is to accrue 30 evaluable patients in each of Part I and Part II of the study and treat them with the experimental AdHER2 vaccine. Unless an early stopping rule is invoked, the number of patients who have experienced a clinically significant cardiac toxicity will be determined to estimate the frequency of cardiac toxicity. In addition, the dose level(s) at which toxicity is observed will also be examined. The statistical rationale for the targeted accrual of 30 patients in each part of the study is outlined in the statistical Section 10.

Dose escalation will proceed in groups of 6 patients. *Dose escalation will proceed as long as 0 to 1 of 6 patients at given dose level have no evidence of toxicity and at least 3 of the 6 patients at the dose level have reached Week 12 on study.* If 2 of 6 patients on any given dose level develop cardiac toxicity, that dose cohort will be closed to further accrual, no higher doses will be explored, and dose expansion of an additional 12 patients will be enrolled in the next lower dose level to further assess for cardiac toxicity. *The vaccine dose at which 0 to 1 of 18 treated patients in Dose Levels 1 to 3 develop cardiac toxicity will be defined as the maximum tolerated dose (MTD). If two or more patients out of 18 at a given dose level have developed cardiac toxicity, then the MTD will have been exceeded at that dose, and the dose level below that one will be considered the MTD.* Since enrollment in Dose Level 3 has been reached and 0 of 6 patients has toxicity, then an expansion cohort of 12 patients, will be added for a maximum targeted accrual of 30 patients in Part I. The 12 patients will be accrued at the  $40 \times 10^6$  dose level without any planned interim stop, as cardiac toxicity is not presently anticipated given the results as of 12/11/15. With all 12 enrolled as a single group, there is a 4.9% probability of having 2 or more of 12 patients with cardiac toxicity if the true probability for a given patient is 3%, and 55.7% of having 2 or more of 12 with cardiac toxicity if the true probability for a given patient is 15%. Therefore, observing 0-1 of 12 with toxicity would be acceptable, and  $40 \times 10^6$  would be considered the maximum evaluated and tolerated dose. If we observe 2 or more with cardiac toxicity at or before accruing the 12th patient, this exceeds a safe level. Further patients would be added subsequently, by amendment, to the next lower dose, to confirm its safety.

If dose escalation has proceeded in the first three dose levels in Part I and 0 of 20 patients have experienced cardiac toxicity, Part II of the study in patients with metastatic breast, gastric, gastroesophageal junction or other cancers and prior exposure to HER2-directed therapies will proceed with vaccine dosing based on the safety confirmed in Part I and outlined in Section 3.1.2. A maximum accrual of 30 patients will be enrolled in Part II.

If no DLTs are observed, then dose levels in Part I and Part II will be assessed for the fraction of patients with immunogenicity and clinical outcomes to determine the biologically optimal vaccine dose that would be used in any future phase II studies involving those respective patient populations.

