- All patients will be given an AdHER2 DC Vaccine Report Card (refer to [Appendix 5](#)) and instructed on how to complete it, following each AdHER2 DC vaccine dose.
- Continued injection of the same forearm is permissible for patients who have one functional forearm or a medical condition that does not allow for continued injections of both forearms.

Since this protocol involves AdHER2 DC vaccination in humans using this vector for the first time, enrollment into subsequent dose level for both Part I and Part II patients will be staggered to allow for safety monitoring as outlined in Section [3.1.2](#): dose escalation will proceed as long as 0 of 6 or 1 of 6 patients within a dose level have no evidence of toxicity and at least 3 of the 6 patients within the same dose level have reached Week 12 on study before enrollment in the next vaccine dose level can begin. If no dose limiting toxicities as defined in Section [3.1.1](#) are observed in the twelve-week window inclusive of the first three vaccinations, enrollment of additional patients may proceed as quickly as is logistically feasible as outlined above and in accordance with the dose escalation parameters outlined in Section [3.1.2](#).

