*Dose escalation will proceed as long as 0 of 6 or 1 of 6 patients within a dose level have no evidence of toxicity and at least 3 of the 6 patients within a level have reached Week 12 on study. If 2 of 6 patients on any given dose level develop cardiac toxicity, that dose cohort will be closed to further accrual, no higher doses will be explored, and dose expansion of an additional 12 patients will be enrolled in the next lower dose level to further assess for cardiac toxicity. The vaccine dose at which 0 to 1 of 18 treated patients in Dose Levels 1 to 3 develop cardiac toxicity will be defined as the maximum tolerated dose (MTD). If two or more patients out of 18 at a given dose have developed cardiac toxicity, then the MTD will have been exceeded at that dose, and the dose level below that one will be considered the MTD. Since enrollment in Dose Level 3 has been reached and 0 of 6 patients has toxicity, then an expansion cohort of an additional 12 patients will be added, for a maximum targeted accrual of 30 patients in Part 1. The Expansion Cohort will be treated at  $40 \times 10^6$  viable cells/vaccine and will be monitored for toxicity in an identical manner as previously identified. The 12 patients will be accrued at the  $40 \times 10^6$  level without any planned interim stop, as cardiac toxicity is not presently anticipated given the results as of 12/11/15. With all 12 enrolled as a single cohort, there is a 4.9% probability of having 2 or more of 12 patients with cardiac toxicity if the true probability for a given patient is 3%, and 55.7% of having 2 or more of 12 with cardiac toxicity if the true probability for a given patient is 15%. Therefore, observing 0-1 of 12 with toxicity would be acceptable, and  $40 \times 10^6$  would be considered the maximum evaluated and tolerated dose. If we observe 2 or more with cardiac toxicity at or before accruing the 12th patient, this exceeds a safe level. Further patients would be added subsequently, by amendment, to the next lower dose, to confirm its safety.*

***To ensure that the trial does not continue to accrue patients in the event that a much greater incidence of toxicity than expected would be recognized early, the following early stopping rules for accrual will be invoked in each part of the study if:***

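### Dose-level decisions count different events: closure and MTD count cardiac toxicity only, while escalation, enrolment and dose selection refer to unqualified toxicity or to any DLT

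*Combined protocol and SAP*

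**What the plan says.** **Definition.** Section 3.1.1 lists as DLTs Grade 2 or higher allergic reactions, "CTCAE Grade 2 and greater autoimmune disorders", cancer therapeutics-related cardiac dysfunction (CTRCD), related Grade 3 or higher organ toxicity within 30 days of vaccination, and Grade 3 or higher anaphylaxis and injection-site reactions.

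**Closure, accrual stop and MTD.** Section 3.1.2 closes a level on cardiac events: "If 2 of 6 patients on any given dose level develop cardiac toxicity, that dose cohort will be closed to further accrual". The MTD sentence is also cardiac. A level qualifies when no more than one "of 18 treated patients in Dose Levels 1 to 3 develop cardiac toxicity will be defined as the maximum tolerated dose (MTD"). The same section then says when a level fails: "If two or more patients out of 18 at a given dose level have developed cardiac toxicity, then the MTD will have been exceeded". Section 11.1 repeats this: "If two or more patients out of 18 at a given dose have developed cardiac toxicity, then the MTD will have been exceeded". The accrual stop in Sections 3.1.1 and 11.1 is two or more of 6 with cardiac toxicity, or a death attributed to the vaccine.

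**Escalation.** Section 3.1.2 drops the word cardiac: "Dose escalation will proceed as long as 0 to 1 of 6 patients at given dose level have no evidence of toxicity". Sections 3.2 and 11.1 carry near-identical sentences.

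**Enrolment.** Section 3.2 says that if none of the Section 3.1.1 DLTs "are observed in the twelve-week window inclusive of the first three vaccinations, enrollment of additional patients may proceed". It does not say what happens if one is observed.

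**The 40 x 10^6 level.** Sections 3.1.2 and 11.1 call 0-1 of 12 with toxicity (unqualified) acceptable and would then name this the maximum evaluated and tolerated dose. The adverse counterpart is cardiac: "If we observe 2 or more with cardiac toxicity at or before accruing the 12" (that is, the twelfth patient), a safe level is exceeded.

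**Optimal dose.** The end of Section 3.1.2 makes the search for a biologically optimal dose conditional on no DLTs being observed.

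**The concern.** In this plan a DLT ends vaccination for the patient who has it (Sections 3.3 and 3.5.1). Whether it also counts against the dose level depends on which sentence is read. Two teams seeing the same two Grade 2 autoimmune events among 6 patients could reach different decisions on escalation and enrolment, and both could cite the protocol.

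The dose conclusion is at stake. Section 1.1.1 opens the primary objective with safety and toxicity in general, and Section 11.1 says vaccine safety will be determined for each dose level. Section 3.2 notes that this vector is being given in humans for the first time, and Section 12.5 acknowledges a potential for autoimmune disease. A reader who sees a dose reported as the MTD will normally take it to reflect all protocol-defined DLTs. Under the closure and MTD wording it reflects cardiac events only.

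**Working it through.** **Step 1. The rules side by side.**

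| Decision | Section | Events counted |
|---|---|---|
| DLT definition | 3.1.1 | Allergic, autoimmune, CTRCD, organ, anaphylaxis, injection site |
| Escalate | 3.1.2, 3.2, 11.1 | Toxicity, unqualified |
| Enrol additional patients | 3.2 | Any 3.1.1 DLT; no action given if one occurs |
| Close a level, bar higher doses | 3.1.2, 11.1 | Cardiac |
| Stop accrual | 3.1.1, 11.1 | Cardiac, or vaccine-related death |
| MTD and MTD exceeded | 3.1.2, 11.1 | Cardiac |
| 40 x 10^6 acceptable | 3.1.2, 11.1 | Toxicity, unqualified |
| 40 x 10^6 unsafe | 3.1.2, 11.1 | Cardiac |
| Part II continuation limit (3 patients) | 11.2 | Cardiac |
| Terminate study for toxicity | 11.4 | CTRCD |
| Optimal-dose assessment | 3.1.2 | No DLTs |

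The escalation sentence has a second problem. Read literally, it requires that 0 to 1 of 6 patients be *free* of toxicity. The evident intent is that at most 1 of 6 *has* toxicity.

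**Step 2. The plan's own figures.** For the 40 x 10^6 level the plan states a 4.9% and 55.7% chance of 2 or more of 12 with cardiac toxicity at true rates of 3% and 15%. With P(X >= 2) = 1 - (1-p)^12 - 12p(1-p)^11:
- p = 0.03: 1 - 0.69384 - 0.25751 = 0.04865, or 4.9%.
- p = 0.15: 1 - 0.14224 - 0.30122 = 0.55654, or 55.7%.

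Both reproduce. The stated operating characteristics are for cardiac events alone.

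**Step 3. How often the event set would matter.** The documents give no non-cardiac DLT rate q, so a range is assumed. For 6 patients, P(X >= 2) = 1 - (1-q)^6 - 6q(1-q)^5:
- q = 5%: 1 - 0.7351 - 0.2321 = 3.3%.
- q = 10%: 1 - 0.5314 - 0.3543 = 11.4%.
- q = 1/3: 1 - 0.0878 - 0.2634 = 64.9%.
- q = 50%: 1 - 0.0156 - 0.0938 = 89.1%.

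In each of these cohorts the closure rule is unaffected. The escalation sentence may or may not be, depending on what toxicity means there.

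**Step 4. Size of the gap at 12 patients.** Assume a 3% cardiac rate and independent non-cardiac DLTs. Counting cardiac events only, 0-1 of 12 occurs with probability 1 - 0.0486 = 95.1%, whatever q is. Counting any DLT at the same cut-off, the per-patient probability is 1 - 0.97(1-q), and 0-1 of 12 occurs with these probabilities:
- q = 10% (combined 0.127): 53.8%.
- q = 20% (combined 0.224): 21.3%.
- q = 33% (combined 0.350): 4.2%.

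Reusing the cardiac cut-off only shows how much depends on the choice of events. It does not propose a rule.

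**The case against.** The strongest reply is that the cardiac focus is deliberate. Section 1.1.1 follows its general safety aim with CTRCD as the only specific safety item. Section 11 states the primary safety objective as whether the cardiac fraction is low enough. Section 1.2.1.2 says the cardiac monitoring plan and the thresholds for discontinuing vaccine were based on FDA recommendations. This stands: a cardiac-only stopping rule is an explained choice, and the point is not that it is wrong.

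A reader might infer that a dose with frequent non-cardiac DLTs would be escalated through and declared tolerated. The documents do not support that. The escalation sentence is unqualified, so on one reading more than 1 of 6 with any toxicity blocks the next dose. The sentence that confers the tolerated label on 40 x 10^6 also omits the word cardiac, although its neighbours include it. Optimal-dose selection is conditional on no DLTs.

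There is also other oversight: staggered enrolment (3.2), weekly team review (7.5.1) and the Safety Monitoring Committee (7.5.2). None of these states a DLT threshold for a dose level, and the committee's scheduled review is only about annual.

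Section 11.3 already promises 80% and 95% intervals for the fraction with toxicity, which could be read as covering all DLTs. The text that follows specifies cardiac fractions only.

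Finally, the matter is partly past. Section 3.1.2 records Part I Dose Level 3 as reached with 0 of 6 having toxicity, so the 2-of-6 rule looks forward mainly to Part II Dose Level 1. The MTD and tolerated labels, and the final tables, are still affected.

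**Conclusion.** The inconsistency is real. Sections 3.1.1, 3.1.2, 3.2 and 11.1-11.2 use at least three event sets (cardiac toxicity, unqualified toxicity and any DLT) for linked dose-level decisions, and Section 3.2 has no branch for an observed DLT. By the letter of the closure and MTD rules, non-cardiac DLTs have no effect on the MTD label. Whether they affect escalation, or the tolerated label at 40 x 10^6, cannot be settled from the text.

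The practical size depends on a rate the documents do not give. Over assumed rates from 5% to 50%, two or more of 6 patients would have a non-cardiac DLT in 3.3% to 89% of cohorts, so the ambiguity could rarely arise or could arise in most cohorts. The point should be addressed, but it does not invalidate the cardiac analysis, whose stated figures for the 40 x 10^6 rule reproduce.

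**What to change.** 1. Reconcile Sections 3.1.1, 3.1.2, 3.2, 11.1 and 11.2 so that each decision (escalation, enrolment, closure, MTD, tolerated label) names the events it counts. Which events these are is for the sponsor and FDA to decide. In the same amendment, reword the escalation sentence so that it says what it means, and state in Section 3.2 what follows when a DLT is observed.
2. In the analysis, report per dose level the fraction of patients with any Section 3.1.1 DLT, with 80% and 95% confidence intervals, beside the cardiac fraction.
3. Wherever a dose is called the MTD or tolerated, state which events the label is based on.

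The cost is amendment wording and one table from data already collected.
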